3.2. Data and Safety Monitoring Committee (DSMC), Dose-Limiting Toxicity, and Stopping Criteria

The purpose of the DSMC is to provide an unbiased review of the safety data generated by the clinical trial. An independent DSMC will be established to review clinical trial data prior to dose escalation and during Part B on an as-needed basis. A statistician, serving as a non-voting member to the DSMC, will provide data preparation support to the DSMC. A sponsor representative will also serve as a non-voting member of the DSMC to facilitate sponsor internal planning.

The Chair of the DSMC will be informed by the Protocol Chair or the Sponsor of the potential need for ad hoc meetings and will coordinate such meetings. A formal DSMC Charter will be prepared and finalized prior to study enrollment.

The DSMC will review all available clinical and laboratory safety data at defined intervals during the conduct of each cohort in Part A and periodically during Part B of the study. Based on a review of available data, the DSMC will make recommendations regarding the continuation, discontinuation or modification of the study, cohort advancement (during Part A), and progression to Part B of the study.

During Part A of the study, the DSMC will apply the following dose-escalation rules per cohort.

- For each cohort, if 0 of the 3 initial evaluable subjects experiences a DLT (see [Section 3.2.1](#) for DLT definition), then escalation may occur to the next higher dose level.
- If 1 of the 3 initial subjects experiences a DLT, then 3 additional subjects will be enrolled at the same dose level for a total of up to 6 evaluable subjects.
- If 1 out of the 6 subjects experience a DLT, then escalation may proceed to the next higher dose level.
- If two (2) or more subjects experience a DLT, no additional subjects will be enrolled in the cohort, and the next lower dose level will enroll additional subjects for a total of 6 evaluable subjects.

The Sponsor will apply the following criteria to the determination of optimal dose in Part A of the study:

- Adequate safety without DLT and

■ [REDACTED]

If more than one dose meets these criteria, then additional safety, tolerability, PK, [REDACTED] and efficacy data will be taken into consideration to select a dose.

DSMC decisions regarding advancement to the next higher cohort will be governed by the principle that the study is not intended to define a maximally tolerated dose (MTD). As such, no further dose escalations will occur once the second of two administered dose levels meet the criteria for an optimal dose, even if the observed safety and tolerability profile of the second (higher) dose level supports further dose escalation.

Additional subjects may be enrolled in cohorts if approved by the DSMC to further characterize drug safety, tolerability, or efficacy. Also, the DSMC may recommend modification of the doses to be evaluated, to not initiate specific dose cohorts, to initiation additional dose cohorts, or to terminate the study if it is deemed necessary. Appropriate regulatory approvals will be obtained prior to initiation of any recommended changes by the DSMC, as required.

3.2.1. Dose-Limiting Toxicities

During the 3+3 dose-escalation of Part A, any of the following events that are considered by the investigator to be at least possibly related to the study drug are considered DLTs during the DLT window Study Days 1–29:

■ [REDACTED]
■ [REDACTED]

3.2.2. Subject Stopping Criteria

Dosing of EQ001 will be permanently discontinued in a subject if any of the following occur:

During Part A:

- Any DLT

■ [REDACTED]
■ [REDACTED]
■ [REDACTED]

During Part B:

- Study drug related toxicity that cannot be controlled with supportive care, despite 1 dose reduction and/or delay of treatment for up to 1 week

During any part of the study:

- Withdrawn consent
- Investigator or Sponsor considers that the subject will not benefit from further investigational product
- Pregnancy
- Subject is not able to comply with the study requirements
- Sponsor terminates the study
- A regulatory authority mandates study dosing cessation

The investigator will classify AEs that are observed in a subject as either expected to occur based on the underlying disease ([Section 7.7](#)) and/or are consistent with the AE profile in the current [EQ001 Investigator's Brochure](#), or unexpected based on their prior clinical experience and management of aGVHD patients.

3.2.3. Study Stopping Criteria

The DSMC can recommend stopping the study at any time based on emerging safety data.

If the recommendation of the DSMC is to halt study dosing for all subjects or pause enrollment, it can be resumed based on the recommendation of the DSMC after further review of all available safety data and notifications of/submitting to appropriate regulatory agencies and institutional review committees, in line with country-specific regulations.

3.3. Rationale for Study Design

The design of this study includes both an open-label (Part A) as well as a double-blinded and placebo-controlled (Part B) component. A two-part study utilizing different designs was chosen to support the attainment of the objectives that are specific to each part of the study.

Part A has been designed to explore the safety and tolerability of ascending dose levels of the IV administration of multiple doses of EQ001. An open-label design is supported by the availability of extensive safety and tolerability data on itolizumab for which to compare the open-label safety data generated in this study. A cohort-based dose escalation design was chosen to rigorously evaluate, and conservatively escalate, IV doses of EQ001. Once a dose is selected in Part A, up to 15 additional subjects will be enrolled at that dose level for additional data.

Part B has been designed to explore the clinical activity of the IV administration of multiple doses of EQ001. A blinded, placebo-controlled design was chosen to provide the most rigorously assessments of efficacy possible in aGVHD.

3.4. Study Duration and Number of Centers

Each subject will have 2 months of treatment and 10 months of follow-up (2 months of safety follow-up and 8 months of long-term follow-up), for a total of 12 months on study.

This study will be conducted at approximately 20 clinical sites in North America. Additional sites and/or countries may be added, depending on subject accrual rates.

4. STUDY POPULATION SELECTION

4.1. Study Population

Each cohort within Part A (dose-escalation), and Part B (double-blind, placebo-controlled), will enroll unique subjects who may not be treated in more than 1 cohort or study part.

4.3. Inclusion Criteria

Subjects must meet all the following inclusion criteria to be eligible for study participation:

1. Male or female subject at least 18 years of age for Part A, and at least 12 years of age for Part B.
2. Recipients of first allogeneic hematopoietic stem cell transplantation (alloHSCT) using myeloablative or non-myeloablative conditioning regimens.

Term	Percentage
GMOs	95
Organic	95
Natural	95
Artificial	75
Organic	95
Natural	95
Artificial	75
Organic	95
Natural	95
Artificial	75
Organic	95
Natural	95
Artificial	75

7. Deemed by the investigator to be likely to comply with the planned procedure as required by the protocol for the duration of the study.

4.4. Exclusion Criteria

Subjects meeting any of the following exclusion criteria are not eligible for study participation:

1. Presence of morphologic relapsed primary malignancy, treatment for relapse after alloHSCT was performed, or requirement for rapid immunosuppressive treatment withdrawal for early malignancy relapse.
2. Evidence of graft failure based on cytopenia(s), and as determined by the investigator.
3. Evidence of post-transplant lymphoproliferative disease

14. As determined by the investigator, any medical, psychiatric, or other condition or circumstance that is likely to negatively affect: the subject's participation in this clinical study, the subject's safety, or the reliability of the study data.

5. STUDY TREATMENT(S)

[figure not shown]
[REDACTED]
[REDACTED]
[REDACTED]
[REDACTED]

5.2. Study Drug

In Part A, all subjects will receive their cohort assigned dose of EQ001. In Part B, subjects will be randomized in a blinded fashion to either EQ001 or placebo using a 2:1 allocation.

The study drugs are:

- EQ001, containing the active ingredient itolizumab (Bmab 600), a humanized recombinant IgG1 mAb that selectively targets the extracellular Sc membrane-distal domain 1 of human CD6 [REDACTED]
- Placebo is a sterile, clear, colorless, preservative-free solution with the same formulation (minus the drug) as EQ001 [REDACTED]

5.3. Treatment(s) Administered

All subjects will receive standard treatment for aGVHD with systemically administered corticosteroids. All subjects must receive their first dose of study drug within 72 hours (3 days) of the subject's initial systemically administered corticosteroid dose.

The systemically administered corticosteroid treatment will be prednisone, at approximately 1-2 mg/kg/day (or its equivalent) at the time of first dose of study drug administration:

5.3.1. Part A

In Part A of this study, EQ001 will be administered every 14 days for two (2) months (5 doses) at the following dose levels:

- Cohort 1: 0.4 mg/kg
- Cohort 2: 0.8 mg/kg
- Cohort 3: 1.6 mg/kg
- Cohort 4: 2.4 mg/kg

See [Section 3.1](#) for additional information regarding dose escalation.

5.3.2. Part B

In Part B of this study, an optimal dose of EQ001 (as identified in Part A) or placebo will be administered in a blinded fashion every 14-days for two (2) months (5 doses). In Part B, study drug will be prepared by an unblinded qualified health care professional (e.g., pharmacist or designee) at the investigative site who is not otherwise associated with the study. Investigators, study site personnel, subjects and the Sponsor and/or designee will be blinded to treatment assignments.

A horizontal bar chart consisting of five solid black bars of increasing length from left to right. The bars are separated by small gaps and are set against a white background.

A thick black horizontal bar, likely a redacted section of a document.

- [REDACTED]
- [REDACTED]
- [REDACTED]
- [REDACTED]

5.4. Prior and Concomitant Medication

Prior and concomitant medications and treatments will be collected from the time the subject signs the informed consent through Day 85. After Day 85 through Day 169, collection of concomitant medications may be required if requested by the Sponsor for any ongoing safety concerns related to study drug.

Prior medications will focus on those used for prevention and treatment of GVHD, including prior investigational treatments.

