In addition, if at any time up to Study Day 169, a subject has an unscheduled study visit, all procedures that were conducted at the visit will be collected in the electronic case report form (eCRF) as an unscheduled visit. If a subject experiences disease progression or recurrence, the subject should complete an unscheduled visit that includes disease assessments and grading.

Safety and Long-Term Follow-Up:

All subjects who complete study drug dosing will be evaluated on Study Day 169 for disease progression assessments, aGVHD organ stages and overall clinical grading, aGVHD-AI, PK [REDACTED], ADA, and AE monitoring .Collection of concomitant medications may be required after Day 85 through Day 169, if requested by the Sponsor for any ongoing safety concerns related to study drug.

During the Long-Term Follow-Up period, the site will phone subjects on Study Days 253 and 337 to collect information on disease status (disease relapse or cGVHD), long-term survival, and safety (eg, recent hospitalization or SAEs).

Dose Modification and Dose Schedule Deviation:

In Part A, if a subject has a DLT during the DLT window (Study Days 1-29), study drug dosing will be discontinued for that subject. Subjects experiencing a DLT will be encouraged to remain in the study and complete the remaining visits; the subjects will not be replaced. If a subject terminates early for a reason other than a toxicity during the DLT window, the subject may be replaced.

In the event of a clinically significant AE that is not a DLT, study drug dosing may be temporarily withheld, and supportive therapy administered, as clinically indicated. If the toxicity resolves to baseline or Grade 1 prior to the next scheduled dose, dosing may be continued at the next scheduled dosing visit as follows, with agreement of the Sponsor and/or Medical Monitor:

- at the assigned dose (subjects in Part A or Part B) or
- at the next lower dose level evaluated in Part A (subjects in Part B only)

Data and Safety Monitoring Committee (DSMC), Dose-Limiting Toxicity, and Stopping Criteria:

A DSMC will review all available clinical and laboratory safety data at defined intervals during the conduct of each cohort in Part A and periodically during Part B of the study. The DSMC will make recommendations regarding the continuation, discontinuation, or modification of the study, cohort advancement (during Part A), and progression to Part B of the study.

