6.9 Clinical Activity

6.9.1 Response to therapy (CR, VGPR, PR, NR, and PD)

At each assessment visit, overall response to therapy will be recorded as complete response (CR), very good partial response (VGPR), partial response (PR), no response (NR), or progressive disease (PD) by the investigator.

Number and percent of subjects with a complete or near complete response (i.e., CR or VGPR) and with any response (i.e., CR, VGPR or PR) will be presented along with 90% exact confidence intervals by assessment visit. If a subject ended treatment prior to an assessment visit that follows immediately after ending treatment, last observed response will be carried forward if the disease assessment was not performed at that visit. However, if the assessment was done but after receiving new aGVHD treatment(s), response will be considered as PD. Disease assessments done after receiving new aGVHD treatments will not be included in summary tables. A bar chart of percent of responders by cohort and visit will be generated. Best overall response (BOR) during the study will also be summarized by BOR category (CR, VGPR, PR, NR and PD). In evaluating BOR for a subject during the study, the hierarchy CR>VGPR>PR>NR>PD will be used where the symbol ' > ' indicating 'better than'. For example, if a subject has a response of NR

[figure not shown]
Statistical Analysis Plan

Sponsor Name: Equillium Inc.

Sponsor Protocol ID: EQ001-aGVHD-001

at Days 15 and 29, VGPR at Day 43, and later progressed (PD), BOR will be VGPR for that subject. A bar chart will also be constructed to graphically display the BOR data.

Further, Day 29 response will be summarized by GVHD clinical grade at screening, worst clinical grade observed on or prior to Day 29 and by categorical grade change (grade worsened, no change, grade improved) from baseline to latest available grade on or prior to Day 29. Additionally, to assess the durability of response seen at Day 29, for subjects with an objective response (i.e., PR or better) at Day 29, disease assessment data will be summarized at assessments done at visits following Day 29.

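### New aGVHD treatment started on Days 86-169 is not routinely recorded, so the Part A SAP's new-treatment rule cannot be applied reliably to it at Day 169

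*Protocol*

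**What the plan says.** **Medication records.** Protocol 5.4 sets the routine window: "Prior and concomitant medications and treatments will be collected from the time the subject signs the informed consent through Day 85". For Day 85 to Day 169 it adds that "collection of concomitant medications may be required if requested by the Sponsor for any ongoing safety concerns related to study drug". The synopsis (Safety and Long-Term Follow-Up) repeats that condition. Protocol 7.5.2 separately puts treatment given for a serious adverse event on the concomitant medication eCRF.

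**Disease assessment.** The same synopsis paragraph states: "All subjects who complete study drug dosing will be evaluated on Study Day 169 for disease progression assessments, aGVHD organ stages and overall clinical grading".

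**Part A analysis.** SAP 6.9.1 has the investigator record response at each assessment visit. It treats new aGVHD therapy in two ways. One sentence follows the carry-forward provision for the visit just after treatment ends: "However, if the assessment was done but after receiving new aGVHD treatment(s), response will be considered as PD". The next is general: "Disease assessments done after receiving new aGVHD treatments will not be included in summary tables". The section also says "Best overall response (BOR) during the study will also be summarized by BOR category", using a hierarchy that ignores the order in which responses occur. For subjects responding at Day 29, "disease assessment data will be summarized at assessments done at visits following Day 29".

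**Longer window.** Protocol 9.9 defines overall response rate as best response of PR or better over 12 months.

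**The concern.** The SAP rule needs one fact about each subject at Day 169: whether a new aGVHD treatment began before the assessment. For a start on Days 86-169 the readable protocol does not require that fact on the eCRF unless the treatment was for an SAE or the sponsor asked on drug-safety grounds. New therapy given because the disease was not controlled is neither of these.

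Two kinds of subject are exposed:

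- A Day 29 responder who flares after Day 85, receives another agent and is in PR or better at Day 169 can appear at that visit as a continuing response.
- A subject with no response through Day 85 who is rescued afterwards can gain a best overall response of PR or better from the rescue therapy.

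Clinical activity is a secondary objective of Part A. The late response summaries would then mix the effect of EQ001 with that of later therapy, and nothing in the analysis data would show it.

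**Working it through.** The plan gives no figure on this point to reproduce. The check sets the passages side by side and adds simple arithmetic.

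**1. Length of the unrecorded window.** Inputs: Day 85 (Protocol 5.4) and Day 169 (synopsis). 169 - 85 = 84 days, that is 84/7 = 12 weeks, or 84/169 = 49.7% of Days 1-169. This is a share of days, not of assessments: the only scheduled response assessment visible after Day 85 is Day 169 itself.

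**2. When the rule works at Day 169.**

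| New aGVHD treatment starts | Routine eCRF record? | SAP 6.9.1 rule at Day 169 |
|---|---|---|
| By Day 85 | Yes (5.4) | Works |
| Days 86-169, given for an SAE | Yes (7.5.2) | Works |
| Days 86-169, other | Only on sponsor request for drug-related safety | Not reliable |

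**3. Which summaries are affected by the third row.**

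- Response at Day 169: yes.
- Durability of the Day 29 response: yes, at its Day 169 assessment.
- Best overall response: only if there was no earlier equal or better response.
- Day 29 response, and the grade and steroid-dose summaries tied to it: no.

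**4. Effect of one misclassified subject.** Shift = 1/n. Cohort and expansion sizes are from Protocol 3.1.

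| n | Shift in response rate |
|---|---|
| 6 (full cohort) | 1/6 = 16.7 points |
| 15 (expansion) | 1/15 = 6.7 points |
| 21 (assumed: 6 + 15 at the selected dose) | 1/21 = 4.8 points |
| 39 (24 + 15, all of Part A) | 1/39 = 2.6 points |

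For scale, using the SAP's 90% exact interval and an assumed 60% rate: 9/15 = 60.0% (36.0 to 80.9) becomes 10/15 = 66.7% (42.3 to 85.8). The shift is well inside the interval, but it is a bias upward, not random error.

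**5. How many subjects.** The documents give no rate of new treatment after Day 85. For best overall response only, expected inflation = (share without response through Day 85) × (share of these starting new treatment on Days 86-169) × (share of those responding at Day 169). All three ranges are assumptions: 20-40%, 5-25% and 30-60%.

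- Low: 0.20 × 0.05 × 0.30 = 0.003, or 0.3 points (0.003 × 39 = 0.1 subjects of 39).
- High: 0.40 × 0.25 × 0.60 = 0.060, or 6.0 points (0.060 × 39 = 2.3 subjects of 39).

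**6. The 12-month rate.** Against the Protocol 9.9 window, the gap is 337 - 85 = 252 days, or 252/337 = 74.8%. The visible content of the Day 253 and 337 calls is relapse or cGVHD, survival and safety. It includes no question on GVHD treatment.

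**The case against.** The strongest reply is that a rescued subject would leave other traces.

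- Protocol 8.13 asks for an unscheduled visit with grading at progression or recurrence up to Day 169. SAP 6.1.2 allows unscheduled data into clinical activity summaries, and SAP 6.9.2 makes progression a PFS event.
- Protocol 5.4.2 has the Medical Monitor told of prohibited therapies, with no Day 85 limit.
- Protocol 10.7 requires medication changes in the progress notes of each clinic visit.
- The Schedule of Events, most of Protocol section 8 and parts of the SAP are withheld, so a Day 169 question on new therapy may exist.

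Much of this stands. A graded flare is visible, and a determined search of source notes could find the treatment. But the unscheduled visit is stated to record the disease, not its treatment, and neither the notification nor the notes are stated to yield a dated analysis record. The withheld pages do limit certainty. Still, the synopsis paragraph that lists the Day 169 evaluations is also the one that makes medication collection conditional, while the Early Termination visit in the same synopsis lists medication recording outright.

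Three stronger readings are tempting, and the documents do not support them:

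- **That the rule fails altogether at Day 169.** It does not: treatment started by Day 85, and SAE treatment later, is recorded.
- **That Part B's primary objective is biased.** Protocol 5.4 covers both parts, but the visible SAP and its new-treatment rule are for Part A. What Part B would do with such subjects cannot be seen.
- **That the steroid-discontinuation endpoint is lost.** The detailed analysis in SAP 6.9.7 counts stopping before an objective response, not tapering through Day 169.

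**Conclusion.** The gap is real but narrow. As written, a non-SAE aGVHD treatment started on Days 86-169 need not reach the eCRF, and the SAP 6.9.1 rule cannot be relied on for it. The Day 169 response and the durability summary are exposed. Best overall response is exposed only for subjects with no earlier equal or better response.

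The firm quantities are the 84-day window and the shift per subject: 16.7 points in a cohort of 6, about 4.8 points if 21 subjects are treated at the selected dose. A reader might infer an overall bias of 5 to 10 points, but that needs 1 to 2 misclassified subjects among 21, and nothing in the documents supplies that count. The 0.3 to 6.0 points shown for best overall response likewise rest wholly on assumed rates.

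The conclusion assumes that the withheld visit schedules and forms contain no dated question on new aGVHD therapy after Day 85. If they do, the remaining problem is that Protocol 5.4 and the synopsis do not mention it.

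**What to change.** 1. In Protocol 5.4 and the synopsis, leave general medication collection at Day 85. Add that all systemic aGVHD therapy (corticosteroid dose changes, new agents, start and stop dates) is recorded for every subject through Day 169, whether or not there is a safety concern. Ask for it at the existing Day 169 visit, on one restricted eCRF page.
2. In SAP 6.9.1, state that the new-treatment rule is applied through Day 169 using those dates. The unrecorded window before Day 169 then falls from 84 days to none.
3. For the 12-month response rate in Protocol 9.9, either ask the same question at the Day 253 and 337 calls, or end the response window at the last visit with treatment data.

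The cost is a wording change and about 12 more weeks of data entry, limited to GVHD drugs. No visit is added and no clinical care changes. A cheaper alternative is to end the affected response summaries at Day 85, which gives up the Day 169 durability information.
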